sampling will be used to select a representative patient group according to age, sex, and race. We anticipate recruiting about 1 patient per week. Patients will be identified when scheduled for surgery. They will receive scripted instruction on the Oculus/Meta Quest and a tutorial on the biofeedback application. Once device and content education are complete, patients will receive manual-based training on the benefits of HRV BF.⁵⁶ They will be given the appropriate equipment and instructed to complete an independent daily, 10-minute session (based on the standard duration of a BF session) and record each session in a log. Patients will bring the equipment to the hospital on the day of surgery for continuation into Aim 1b. After surgery, patients will have free use of VR-BF. They will be instructed to undergo, at minimum, one daily, 10-minute session. They will also be instructed to freely use VR-BF, particularly when in pain. They will use a log to record their VR-BF usage (date, time, and duration). Patients will be visited daily, or more or less frequently as applicable/needed, to assist with log completion and any issues. On the day of discharge, a study team member will conduct a detailed, semi-structured interview. Patients may take the VR-BF device home for up to two weeks for home pain management; a similar log will be used to document home use. We will enroll 4 patients at a time and analyze data to refine the protocol in an iterative fashion; this process will be repeated until 12 patients are enrolled. If further data is required for protocol refinement, we will continue recruiting patients in groups of 4 as necessary until a maximum number of 32 patients is reached.

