Research Design (Figure 3). Eligibility, recruitment, and study procedures will follow those described in Aim 1 but VR-BF or the control condition will be applied both pre- and

postoperatively according to the protocol refined in Phase 1. Figure 3 summarizes Aim 2 design. During the preoperative visit with our study team, patients randomized to the control group will download the *Manage My Pain* application onto their device. If patients do not have a personal device, we will ask a parent to download the program onto his or her phone or computer. We will provide explicit instructions on how to use the application and what features should be used. Patients will also be instructed on how to create a daily report documenting each day's use of the application prior to surgery. These daily reports will be returned to our study team. Like the VR-BF group, patients will receive scripted instruction on the benefits of mind body therapy, will be instructed to use the application for at least 10-minutes per day for seven days prior to surgery, and will be asked to complete a daily report using the application each day. On the day of surgery, a study team member will visit each participant to document possession of the FOREVR VR platform (intervention group), to collect reports, and to any answer questions.

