After surgery, as in Aim 1, a trained CRC will visit patients daily or as needed while hospitalized. Control group patients will complete a daily application-generated usage report (date, time, duration); VR-BF patients will have this information, along with HRV and respiratory rate data, obtained from the device. To help determine what outcomes may be impacted by VR-BF for future trial development, patients will also be asked to document pain and anxiety scores before and after each VR-BF or application session using the NRS.^{110,111} Patients will self-report and document these scores before each session and then immediately, 15 minutes, and 30 minutes after session completion. All pain scores and opioid consumption (in morphine equivalents mg/kg/day) will be collected from EPIC, the electronic medical record, for each 24-hour period during study enrollment; anxiety scores are not documented by the nursing staff so only self-reported scores will be used. Documented pain scores will also help finalize the “dose” of VR-BF to be used in the efficacy trial as we will assess for correlation, if any, between pain score and use of VR-BF. At the final study visit prior to discharge, patients will answer a questionnaire and engage in a semi-structured interview soliciting qualitative feedback about their experience with the intervention or control to finalize the study protocol for the clinical efficacy trial. Participants will be given the option to take the VR-BF platform home or continue using the *Manage My Pain* application for up to two weeks after discharge. If this option is selected, patients will complete a daily log/report documenting use, pain scores, and opioid consumption. During the first postoperative clinic visit, VR-BF and reports/logs will be collected and questions about home use will be asked, answered, and recorded. Parents will also be asked to complete a survey about their experience and opinions. If patients cannot be met during the first postoperative clinic visits, other arrangements will be made to collect the information and equipment.

Feasibility and Acceptability of Technology-Based Interventions in the Perioperative Setting

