Dosing. To finalize VR-BF dosing prior to the efficacy trial, data will be collected on the number of daily practice (preoperative) and therapy (postoperative) sessions completed by each patient, duration of each session, changes in HRV and respiratory rate, and achievement of target HRV and respiratory rate parameters. We will also assess the total daily dose of sessions by totaling the duration of all sessions per day and assessing the mean and variability of the total daily dose. Achievement of target physiological parameters will be assessed by calculating the percentage of time a patient spends within specified targets for each session. Consistency in achieving target HRV and respiratory rate parameters will be defined as a binary outcome (yes/no) when the target range is achieved $\geq 75\%$ of the time during use (by session and by day). We will run descriptive statistics on duration of each session stratified by sessions achieving consistency (or not) and on frequency and duration of daily use by days achieving consistency (or not). Mean duration per session and mean duration and frequency per day in the group achieving consistency will be used to guide minimal dosing in the efficacy trial. **Exploratory analysis.** We will examine the association of VR-BF dose (frequency and duration of use) with the change in target physiological parameters to help identify the minimal dose (frequency and duration of use) required to reach consistency in achieving these targets. We will also examine the correlation between pain score reduction and VR-BF use (frequency and duration). We will calculate mean changes in pain score before and after VR-BF and mean frequency and duration of VR-BF use for each patient. We will visualize any correlation using a scatter or box plot and quantify the correlation using Spearman or Pearson correlation coefficients between two continuous variables

Feasibility and Acceptability of Technology-Based Interventions in the Perioperative Setting

and two sample t-tests or Wilcoxon rank-sum tests, as appropriate, between a continuous and categorical variable. Regression on changes in pain score will be used to examine linear or nonlinear correlations between pain reduction and VR-BF use. The same analysis will be repeated for opioid use (mg/kg/day) and patient-reported anxiety scores.

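### The exploratory analysis of pain change by VR-BF use omits pre-session pain, so starting pain can create, hide or reverse an apparent dose-response

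*Combined protocol and SAP*

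**What the plan says.** The analysis is in Section 17.0, Aim 2, in the exploratory part of the dosing paragraph. Pain change and use are each reduced to a patient mean: "We will calculate mean changes in pain score before and after VR-BF and mean frequency and duration of VR-BF use for each patient". They are correlated (Spearman or Pearson), and then "Regression on changes in pain score will be used to examine linear or nonlinear correlations between pain reduction and VR-BF use". No covariate is named. The same analysis is to be repeated for anxiety and for opioid use.

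Use is tied to pain in Section 6.0, Aim 1 Research Design. There is a floor, "They will be instructed to undergo, at minimum, one daily, 10-minute session", and above it use is self-selected: "They will also be instructed to freely use VR-BF, particularly when in pain". For Aim 2, "Eligibility, recruitment, and study procedures will follow those described in Aim 1", except that the intervention is applied according to the protocol refined in Phase 1.

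The missing covariate is collected in both arms (Section 6.0, Aim 2 Research Design): "Patients will self-report and document these scores before each session and then immediately, 15 minutes, and 30 minutes after session completion". The same passage gives documented pain scores a role in finalizing the dose for the efficacy trial, because "we will assess for correlation, if any, between pain score and use of VR-BF".

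**The concern.** A patient in more pain has been told to use the device more. If the fall after a session also depends on how high pain was beforehand, starting pain is a common cause of both variables in the correlation. The coefficient then mixes any effect of using VR-BF more often with a difference in who uses it more often, and the planned output offers no way to separate them.

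At stake is the reading of one input to the efficacy-trial dose. A positive coefficient would suggest that more use brings more relief. A null or negative one would suggest that extra use adds nothing. Either could arise from starting pain alone.

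**Working it through.** **Plan's own figure.** The documents give no figure for this analysis. The only design figure is the sample size (Section 17.0, Aim 2). The exact 95% CI for 80% at n = 56 is 0.672 to 0.895, width 0.223, which rounds to the stated 0.22; 56/0.8 = 70 enrolled. So 35 × 0.8 = 28 VR-BF patients are expected in the analysis.

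**Inputs from the documents.** VR-BF pilot pain intensity has mean 5.11 and SD 1.74, with a fall of about 1 point immediately after one session (Section 3.0, pilot data); at least one session per day; n = 28.

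**Assumptions not in the documents.** Half the pain variance is between patients, so the between-patient SD is 1.74 × √0.5 = 1.23. There are 4 inpatient days and on average 1 extra session per day. The log rate of extra sessions rises by *a* per between-patient SD of pain. Post-session noise has SD 1. Scores are rounded and kept within 0 to 10.

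**Expected bias by formula.** If the fall is 20% of pre-session pain and frequency has no effect, the unadjusted slope of fall on sessions per day is

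slope = 0.2 × Cov(pain, frequency) / Var(frequency),

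with Cov = *a* × 1.23 and Var = (exp(*a*²) − 1) + 1/4.

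- *a* = 0.3: 0.2 × 0.369 / (0.094 + 0.25) = 0.21 points per daily session.
- *a* = 0.6: 0.2 × 0.738 / (0.433 + 0.25) = 0.22 points per daily session.

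The true slope is zero in both cases.

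**Simulation.** 1,000 runs per row, true dose effect zero. The adjusted analysis adds the patient's mean pre-session pain to the regression.

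| How pain change behaves | *a* | Mean r | p<0.05, unadjusted | Slope, unadjusted | Slope, adjusted | p<0.05, adjusted |
|---|---|---|---|---|---|---|
| 20% of pre-session pain | 0.3 | 0.27 | 29.8% | 0.22 | -0.01 | 4.2% |
| 20% of pre-session pain | 0.6 | 0.37 | 51.8% | 0.23 | -0.02 | 3.9% |
| Constant 1-point fall | 0.3 | 0.03 | 5.5% | 0.02 | -0.01 | 5.4% |
| Constant 1-point fall | 0.6 | 0.03 | 2.6% | 0.02 | -0.02 | 3.8% |
| No effect, extra sessions at pain peaks | 0.3 | 0.05 | 6.0% | 0.04 | -0.03 | 5.7% |
| No effect, extra sessions at pain peaks | 0.6 | 0.12 | 6.7% | 0.07 | -0.06 | 6.0% |
| Higher-pain patients respond less | 0.3 | -0.24 | 25.0% | -0.19 | -0.05 | 5.3% |
| Higher-pain patients respond less | 0.6 | -0.35 | 48.0% | -0.20 | -0.09 | 7.8% |

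The simulated slopes under the proportional fall (0.22, 0.23) agree with the formula. With *a* = 0, so that use is unrelated to pain, r is about 0 in every scenario.

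A separate null simulation at n = 28 gave r = 0.27 to 0.40 and p<0.05 in 27% to 61% of runs under the 20% proportional fall (about 4% after adjustment), 3% to 5% with a constant fall, and 3% to 4% with no effect.

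**Limits of the check.** Only frequency was examined, not duration. The adjustment tested was the patient-mean version, not a session-level model. It did not fully remove the bias in the last two scenarios (adjusted slopes -0.03 to -0.09).

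**The case against.** **The bias is conditional.** A reader might infer that a false positive dose-response will certainly appear. The documents do not support that. It requires use that truly varies with pain and a fall that grows with starting pain. The pilot section reports only mean falls for the group as a whole, never change by starting pain level, and a fall of about 1 point fits a constant fall as well as a proportional one. This stands, and it is why the point is one of unknown direction. A constant fall is less plausible for anxiety, though: the VR-BF pilot mean is 2.05 (SD 2.50), only 2.05/2.50 = 0.82 SD above zero, against 5.11/1.74 = 2.94 SD for pain, so many patients have little room to fall by the pilot's 0.9 points.

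**The rates depend on the settings.** With 35 patients and other assumed settings, the proportional fall gave 76% to 92%. When patients reacted to pain relative to their own usual level, the rate was about 13%. No single rate should be quoted as the plan's error rate.

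**The instruction belongs to Aim 1.** Frequency and duration are what Phase 1 refines, so the Aim 2 instruction may differ. This stands as a qualifier; nothing in the current text withdraws the instruction.

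**The consequence is limited.** A reader might infer that the efficacy-trial dose rests on this correlation. It does not: minimal dosing is guided by use in the group that consistently achieves its HRV and respiratory targets. Section 17.0 also rules out tests on clinical outcomes and confirmatory testing, so p<0.05 is only a yardstick here, although the exploratory paragraph does name t-tests and Wilcoxon tests. Section 6.0 still gives pain scores a part in finalizing the dose, and a biased coefficient misleads without a p-value.

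**The plan already looks at pain against use.** That would reveal the link between the two but would not remove it from the analysis of change.

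**Adjustment can remove real benefit.** If sessions have a lasting effect, later pain scores carry it. With an assumed lasting fall of 0.15 points per session, the total effect of frequency was about -0.23 to -0.29 points per daily session, while a patient-mean adjustment that included pain over the stay returned about 0. The raw correlation misses that effect too. This stands and narrows the remedy.

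**Conclusion.** The point holds in conditional form. The planned association between pain change and use omits a recorded variable that, under the current instruction, may influence both. With no true dose effect and about 28 patients, mean r ranged from about -0.35 to +0.40 according to how the fall depends on starting pain. Under a 20% proportional fall, p<0.05 occurred in about 27% to 61% of runs; with a constant fall or no effect it stayed at roughly 3% to 7%. All of this assumes that use rises with pain, with a between-patient variance share and a distribution of use that the documents do not give.

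The planned analysis cannot show which case applies. It merits correction because the remedy needs no new data, but it is a weakness in an exploratory analysis and leaves the feasibility conclusions untouched.

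**What to change.** In Section 17.0, Aim 2, exploratory analysis:

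- Keep the raw correlation, labelled as a description.
- Add a session-level model of post-session pain, at a stated post-session time, on frequency and duration of use. Adjust for pre-session pain, entering its patient-mean and within-patient parts separately, and include a patient random effect. Do the same for anxiety with pre-session anxiety.
- Do not adjust for mean medical-record pain over the stay, which is measured after earlier sessions. Do not report a partial correlation, which is not uniquely defined for a mixed model.
- Show the same model for control-app sessions beside it; the plan already has patients rate them: "patients will also be asked to document pain and anxiety scores before and after each VR-BF or application session".
- Report the results as descriptive, and say in Section 6.0 that any pain-related input to dose finalization uses the adjusted estimate.

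The cost is analysis wording and one or two degrees of freedom with about 28 to 35 VR-BF patients. Later pre-session scores may still carry some lasting benefit of earlier sessions, so the adjusted estimate describes within-session relief only and is not causal. Opioid use is collected per 24-hour period and has no pre-session value, so this change does not cover it.

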Reduction of pain and anxiety with VR-D. Children and adolescents (8-18 years) being managed by Cincinnati Children’s Hospital Acute Pain Service for moderate to severe pain after surgery were screened for eligibility. Over seven months, we enrolled 50 patients to participate in a single, 10-minute postoperative VR-D session (Table 1). After consent, patients were asked to complete surveys for

Feasibility and Acceptability of Technology-Based Interventions in the Perioperative Setting

trait measures: (a) pain catastrophizing (Pain Catastrophizing Scale for Children, PCS-C)¹⁰⁷ and (b) anxiety sensitivity (Child Anxiety Sensitivity Index, CASI).^{108,109} Children played one of three games (all provided a similar distraction-based experience) for ten minutes. Patients were asked to rate their pain intensity, pain unpleasantness, and anxiety using the numerical rating scale (NRS)^{110,111} immediately and 15 and 30 minutes after the VR session. Pain intensity decreased by about 1 point immediately following the session ($p<0.0001$), and this change remained significant at 15 minutes (0.4 points, $p=0.02$) but not at 30 minutes. Pain unpleasantness decreased significantly (1.5 points, $p<0.0001$) immediately following the VR-D session and this change remained significant at 15 (0.8 points, $p=0.0008$) and 30 minutes (0.33 points, $p=0.0001$) following session completion. We found only minimal associations of VR-D with anxiety. Anxiety decreased from baseline by about 1 point immediately following the session ($p<0.0001$) and remained lower at 15 minutes (0.4 points, $p=0.0014$) but was no longer significant at 30 minutes. Levels of pain catastrophizing and anxiety sensitivity were not associated with changes in pain and anxiety. No patients experienced adverse effects related to VR-D. Small, transient changes in pain and anxiety were associated with a single, 10-minute postoperative VR-D session. These results informed our decision to explore integration of a mind-body therapy with VR using a commercially available VR application.

Reduction of pain and anxiety with VR-BF. In a follow-up study, patients (n=51) were recruited from the Acute Pain Service over 8 months (Table 1) using the same eligibility criteria

[figure not shown]

Figure 2. Changes in pain following VR-BF.
Figure provided for graphical purposes only.

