Feasibility. We will calculate descriptive data on 1) How many patients are screened per month; 2) Percentage of patients meeting eligibility criteria; 3) Percentage of eligible patients approached, enrolled, and randomized; 4) Percentage of patients completing Phase 2; and 5) Percentage of patients adhering to preoperative education and postoperative application of VR-BF as defined in the study measures. For each measure, the rates, variances, and two-sided 95% confidence interval (CI) will be reported. Each CI will be examined to determine if the hypothesized value of 80% is contained within the interval. This data will also be used to generate a diagram of participant flow. Because this is a feasibility study, we will not conduct statistical tests on the clinical outcomes collected for exploratory purposes (pain and anxiety ratings, opioid use). We will analyze this data using descriptive measures stratified by treatment arm. **Acceptability.** We will calculate descriptive data on 1) Treatment/study burden: number and percentage of patients completing all study measures; 2) Tolerability: number and percentage of patients experiencing AEs; and 3) Any quantitative data of satisfaction and treatment credibility from questionnaires and semi-structured interviews. For each of these measures, the rates, variances, and two-sided 95% CI will be reported. The CI for treatment/study burden will be examined to determine if the hypothesized value of 80% is contained within the interval. Qualitative treatment credibility and parent/patient satisfaction data will be assessed qualitatively as described below.

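### The exploratory pain-by-use analysis is fitted in the VR-BF arm only, so session length cannot be separated from the time elapsed between the two scores

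*Combined protocol and SAP*

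**What the plan says.** Section 17.0 (Aim 2, Exploratory analysis) sets the question: "We will also examine the correlation between pain score reduction and VR-BF use (frequency and duration"). It builds the variables as follows: "We will calculate mean changes in pain score before and after VR-BF and mean frequency and duration of VR-BF use for each patient". It then adds: "Regression on changes in pain score will be used to examine linear or nonlinear correlations between pain reduction and VR-BF use". Each of these is defined on VR-BF use, so a control patient has no value to contribute. No arm term, pre-session score or elapsed-time term is named. The analysis is to be repeated for anxiety scores and for daily opioid use. The paragraph does not say which post-session score forms the change. Nor does it say whether duration means the length of a session or the daily total, which the Dosing paragraph just before it also derives.

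Section 6.0 (Aim 2, Research Design) fixes the timing: "Patients will self-report and document these scores before each session and then immediately, 15 minutes, and 30 minutes after session completion". The scores are taken in both arms: "patients will also be asked to document pain and anxiety scores before and after each VR-BF or application session using the NRS". Session length is also available for controls: "Control group patients will complete a daily application-generated usage report (date, time, duration"). The only stated use of control-arm pain and anxiety data is in the Feasibility paragraph of section 17.0: "We will analyze this data using descriptive measures stratified by treatment arm". Section 6.0 also names the correlation between pain and VR-BF use as one input to the dose carried into the efficacy trial.

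**The concern.** The later scores are timed from the end of the session. The gap between the first and a later score is therefore the session length plus 0, 15 or 30 minutes. Within one arm, a patient with longer sessions is also a patient whose two scores lie further apart. If pain settles over that interval for reasons unrelated to biofeedback, the settling appears as a slope on session duration and can be read as a dose effect. Such settling is plausible. In Aim 1 patients are told to use the device especially when they hurt, and Aim 2 procedures follow Aim 1 as refined. Sessions may therefore start near pain peaks, yet the pre-session score is not in the model.

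At stake is one of the inputs to the choice of session length for the efficacy trial. The randomised control arm supplies the same scores and durations and could show how much of the slope is non-specific, but the plan does not use it for this.

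**Working it through.** **1. What the slope estimates.** Let D be session length, k = 0, 15 or 30 minutes, δ the shared change per minute (negative if pain falls), β the VR-BF dose effect per minute and γ any effect of the app per minute.

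- VR-BF arm: change = a + δ(D + k) + βD + error, so the slope on D is δ + β.
- Control arm: the slope on D is δ + γ.
- Arm-by-duration difference: β − γ.

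The constant k moves the intercept only, so the choice of post-session score does not remove δ from a linear slope. The algebra concerns per-session D. Sessions per day, total minutes per day and opioid mg/kg/day are not intervals between two scores.

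**2. Inputs.** The plan states no figure for this analysis. Group size follows from section 17.0: 70 × 0.80 = 56 analysed, 28 per arm. The exact 95% CI at n = 56 and 80% is 0.672 to 0.895, width 0.223, which agrees with the plan's 0.22. Not in the documents, and assumed: residual SD of a patient mean 1.0 point, mean session 10 minutes (truncated below at 2), between-patient SD of duration 3, 5 or 10 minutes, and a shared fall of 0 to 0.10 points/min.

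**3. Simulation with β = γ = 0** (4,000 trials per cell, 28 per arm, nominal two-sided 5%). Entries are rejection rates for the VR-BF-only slope.

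| Shared fall (points/min) | SD 3 | SD 5 | SD 10 |
|---|---|---|---|
| 0 | 5% | 5% | 5% |
| 0.01 | 5% | 5% | 7% |
| 0.02 | 6% | 8% | 13% |
| 0.05 | 11% | 22% | 52% |
| 0.10 | 31% | 66% | 97% |

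At SD 5 the mean estimated slope equals the shared fall: −0.021, −0.050 and −0.100 for falls of 0.02, 0.05 and 0.10. With the 30-minute score and a fall of 0.05 it is −0.051. The arm-by-duration term rejects in 4.5-5.5% of trials in every cell. Its empirical SE at SD 5 is 0.059 against 0.042 for the single-arm slope, a ratio of about 1.4, as √2 predicts for equal arms.

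**4. Does adjusting for pre-session pain suffice?** A second simulation used 8 sessions per patient, mean session 12 minutes, patient-effect SD 0.8 and session-error SD 2.0. These give a patient-mean SD of √(0.8² + 2.0²/8) = 1.07 and a single-session SD of √(0.8² + 2.0²) = 2.15. The VR-BF pilot (fall of about 1 point, p = 0.002, n = 51) implies 1 × √51 / 3.26 = 2.19. At 35 per arm and duration SD 5, VR-BF-only rejection was 8.0% unadjusted and 8.4% adjusted at 0.02, and 22.1% and 24.2% at 0.05. At 28 per arm the unadjusted figure at 0.05 was 19%. Over duration SDs of 2.5 to 7.5 minutes the range at 0.02 was 5-10%. Adjustment in one arm does not separate δ from β.

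**5. Which falls are plausible?** For distraction VR, section 3.0 reports: "Pain intensity decreased by about 1 point immediately following the session". From the immediate to the 30-minute score, a continuing trend would add 30 × 0.02 = 0.6, 30 × 0.05 = 1.5 or 30 × 0.10 = 3.0 points. Instead, the fall in intensity with distraction VR shrank from about 1 to 0.4 and then to non-significance. With VR-BF it was about 1, non-significant, then about 1. The only later value larger than the immediate one is VR-BF unpleasantness, 1.5 to 2 points: 0.5/30 = 0.017 points/min.

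**The case against.** The strongest reply has four parts.

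- **Role of the analysis.** It is labelled exploratory, the plan disclaims confirmatory testing, and minimal dosing is guided by sessions and days that reach the physiological targets. A 5% rejection rate is not a decision rule in the plan. This stands and limits the consequence. It does not change what the slope means when it is read alongside the other inputs.
- **Size.** The pilot gives no sign of a continuing fall at 0.05 or 0.10 points/min. Session lengths may also vary little, since the planned game lasts up to 10 minutes, the back-up narrative 10 minutes, and the instructed sessions are about that long. This stands. The SD 10 column and the bottom row of the table are not realistic cases.
- **The comparator.** The app does not reproduce VR immersion and asks patients to reflect on their pain, so γ may not be zero. Session length is self-selected in both arms. This stands too. The difference estimates β − γ, not β.
- **Precision.** With a true effect of 0.05 points/min and no drift, the interaction was detected in about 13% of simulated trials, against 23% for the single-arm slope. That argues for reporting both slopes as estimates, not for leaving out the control slope.

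**Conclusion.** The point holds for per-session duration, for pain and anxiety. As written, the VR-BF-only slope is the sum of any biofeedback dose effect and any other change over the same minutes, and nothing in the single-arm model separates them. The size cannot be computed from the documents, because no untreated or control pain course is reported. On the assumed inputs, rejection is about 5-10% at 0.02 points/min. It is about 20% at 0.05 points/min with a duration SD of 5 minutes. The pilot favours the smaller figure.

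A reader might infer more, and the documents do not support it:

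- That the pilot's fall of about 1 point over a 10-minute session measures a drift of 0.1 points/min. Neither pilot had an untreated arm, and the later intensity scores do not keep falling.
- That every use measure is affected. Frequency, daily total duration and daily opioid use are not.
- That the efficacy-trial dose will be biased upward. No section sets session length from this slope alone.
- That the VR-BF slope should be set aside unless it exceeds the control slope. With a non-neutral comparator and a larger SE, that gate is too strict for a pilot.

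**What to change.** In section 17.0, Aim 2, Exploratory analysis:

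1. State whether duration is per session or per day, and which post-session score (immediate, 15 or 30 minutes) forms the change.
2. For pain and anxiety, fit change = arm + session duration + arm × duration + pre-session score, using both arms.
3. Report the VR-BF slope, the control slope and their difference with 95% CIs, as exploratory estimates. This also sits better with the Feasibility paragraph, which rules out statistical tests on these outcomes.
4. State that the VR-BF-only slope will not be interpreted as a VR-BF-specific dose effect without the control slope beside it.

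The cost is analysis wording. The control scores, session times and durations are already collected, so there is no added patient burden. The plan should state the downsides: the difference has an SE about 1.4 times that of the single-arm slope, session length is self-selected in both arms, and the app neither controls for immersion nor is guaranteed to leave pain unchanged. If longer app use itself relieves pain, the difference understates the VR-BF slope.
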